Feasibility and Acceptability of Using Low-Gain Hearing Aids for Bothersome Tinnitus

NCT03904264

March 20, 2019

Research Protocol

Title

Feasibility and Acceptability of Using Low-Gain Hearing Aids for Bothersome Tinnitus

Investigators

Principal Investigator: [name], Au.D.

Specific Aims/Purpose

The study team will obtain pilot data evaluating Veterans with normal hearing thresholds through 4 kilohertz (kHz) and bothersome tinnitus to determine if low-gain hearing aids for tinnitus is an acceptable and feasible approach to addressing bothersome tinnitus, and to provide preliminary data on the impact of providing mild amplification on perceived tinnitus handicap and perceived hearing handicap in the population being studied. This pilot study will also include interviews of clinical audiologists who both are and are not fitting mild amplification for tinnitus on patients with normal hearing. This study is the essential first step toward fully investigating the premise that low-gain hearing aids are effective for individuals who have bothersome tinnitus but who otherwise are not hearing aid candidates.

The project has two Specific Aims.

Aim 1: Measure the reduction in tinnitus handicap when mild amplification through receiver-in-the-canal hearing aids is provided to Veterans with bothersome tinnitus and normal hearing thresholds through 4 kHz.

Aim 2: Document the opinions, procedures, and rationale used clinically to make decisions regarding fitting mild amplification for tinnitus on Veterans with bothersome tinnitus and normal hearing thresholds.

Hypothesis: This pilot study is not hypothesis driven.

Scientific Rationale and Significance

Tinnitus affects 10-15% of the adult population¹. Of this population, approximately 80% do not seek tinnitus-specific clinical services^{2, 3}. For the remaining 20%, however, tinnitus impacts their lives—most broadly with respect to sleep disturbance, impaired concentration, and/or emotional reactions⁴. Those 20% are the most in need of clinical services. Approximately 80% of all people with tinnitus (not just those looking for help with tinnitus) also have hearing loss⁵. However, people with tinnitus and normal hearing can also be very bothered by their tinnitus. A recent summary of evidence-based tinnitus clinical practice guidelines from The United States, Germany, The Netherlands, Sweden, and Denmark all recommend use of hearing aids, “but only when clinically meaningful hearing loss is also present”⁶ (p. 9). Tinnitus clinical practice guidelines are based on available evidence from well-designed trials. Currently there are no trials of hearing aids for tinnitus in people with normal hearing sensitivity. Because of this, the guidelines from the United States, Germany, and the Netherlands caution that there is insufficient evidence to support the use of hearing aids for tinnitus in people with normal hearing, and Germany’s guidelines recommend against the practice⁶.

Despite the current tinnitus practice guidelines, there are increasing reports from the field that audiologists are providing mild amplification through hearing aids for bothersome tinnitus to patients who have normal hearing sensitivity. Clinicians are informally reporting beneficial outcomes from the practice, and at least one clinician has presented the procedures and outcomes of this practice at a professional conference⁷. Further evidence that clinicians are warming up to the idea of fitting hearing aids for the purposes of addressing tinnitus when

hearing is not a problem comes from a three-round Delphi review of hearing professionals from the United Kingdom⁸. Of the 28 panelists who were interviewed, 82% agreed that “hearing aids should be offered for patients with a mild loss and bothersome tinnitus even if they did not report hearing difficulties”⁸ (p. 7).

There is some limited, published, evidence that patients with normal hearing thresholds are willing to use mild amplification, and that is safe to do so. A study was conducted in which 19 subjects with normal hearing threshold were fit with hearing aids adjusted to provide mild amplification⁶. The amplification was being provided for the purposes of addressing reported hearing handicap. Seventeen subjects completed the trial period and their hearing thresholds were tested at the beginning and end of the trial with no change in thresholds. Of the original 19 subjects, one dropped out the study because he found the hearing aids to be too loud, and one was dropped from the study because he lost one of the hearing aids. Of the 17 who remained in the study, data logging indicated that they were wearing the hearing aids approximately 1-4 hours per day. Hobson et al⁹ concluded, based on their review of numerous studies, that hearing aids used for tinnitus management did not present any safety concerns.

There is considerable evidence that providing amplification through hearing aids for people with hearing loss can be beneficial in reducing functional effects of tinnitus¹⁰⁻¹³. Statistically validated tinnitus outcomes instruments are all vulnerable to influence from improvements in hearing function, which makes it difficult to separate the effects of improved communication from improvements in function that are independent of hearing problems. In a summary of use of hearing aids and sound generators for tinnitus in people with hearing loss, Hoare et al¹⁴ acknowledged that “It is uncertain what benefit from hearing aids results from a change in reactions to tinnitus as opposed to improvement in hearing function” (p. 68). We do however have reasons to believe that hearing aids may be helpful for tinnitus even when there is no hearing problem to be addressed. Hoare et al suggested three possible mechanisms whereby hearing aids could be beneficial for tinnitus for reasons not related to improved hearing function: (1) Amplifying external sounds reduces the contrast between tinnitus and the ambient sound environment, thereby making the tinnitus less salient. (2) Amplification may facilitate refocusing attention onto external sounds. (3) Amplification enriches the sound environment, restoring afferent input to the central auditory system and reducing the opportunity for neuroplastic changes that may contribute to tinnitus generation. In addition, two studies have supported the premise that hearing aids may provide benefit for bothersome tinnitus that is similar to ear-level sound generators: (1) Parazzini et al¹⁵ compared the use of hearing aids to sound generators when delivering tinnitus retaining therapy¹⁶. Despite the lack of significant hearing loss in the speech-frequency range, both sound generators and hearing aids provided identical and significant improvement. (2) Folmer and Carroll¹⁷ showed that hearing aids and sound generators both achieved significant improvement, whereas control subjects (not using devices) did not benefit. One potential benefit of using hearing aids to provide sound stimulation for tinnitus is that the sound provided from hearing aids would be unlikely to make it more difficult to communicate, which may not be the case with ear level sound generators.

The procedures used to provide mild amplification as reported at the 2017 JDVAC⁷ are consistent with those described via personal communication with various other clinicians, i.e., the hearing aids provide approximately 5-10 decibels (dB) of gain as verified by real-ear measurements. Several clinicians mentioned they were using National Acoustic Laboratories Non-linear 2 (NAL-NL2) prescriptive targets for normal thresholds, which approximates 5-10 dB of gain. Other clinicians report they are providing 5-6 dB of gain. Each of these methods for choosing target gain results in similar outcomes. Most clinicians who were informally queried also reported that they ensure that the maximum output of the hearing aids is minimized, and that there is no amplification for 80 dB inputs. All clinicians reported using open-fit receiver-in-

canal hearing aids. These informally collected guidelines are in accordance with the fitting strategy used in a study of hearing aids fit on people who had normal hearing but reported hearing difficulties¹⁸; amplification in those cases was adjusted to 5-10 dB of insertion gain from 1 kilohertz (kHz) through 4 kHz for soft and conversational inputs, with no amplification at loud inputs.

The use of hearing aids for individuals with bothersome tinnitus and normal hearing is reported by many audiologists to be successful. Audiologists use varying methods to determine the success of the practice, including patient reports of satisfaction, tinnitus outcome instruments, and hearing outcome instruments. However, no systematic study of the feasibility, acceptability, or efficacy of this approach has been conducted. It is essential to show evidence supporting such practice in order to justify the continued use (and expense) of fitting these devices to patients who otherwise do not qualify to receive hearing aids. This is especially important in Veterans whose quality of life suffers from tinnitus, which is the most prevalent service-connected disability¹⁹, and for the Veterans Health Administration. The anecdotal nature of the existing evidence suggests the need for pilot data to determine if a randomized controlled trial (RCT) is warranted and, if so, how to conduct the study. Data from this pilot study will provide critical information regarding recruitment rates of Veterans with normal hearing thresholds through 4 kHz and bothersome tinnitus, compliance and acceptability of the procedures with the target population, and will help to determine if existing tinnitus and hearing outcome instruments are appropriate for use with the target population.

Department of Veterans Affairs (VA) audiologists who have adopted the practice of fitting low-gain hearing aids to Veterans with normal hearing and bothersome tinnitus have each developed procedures for identifying appropriate candidates, fitting the devices, and evaluating outcomes. Their collective experiences comprise a valuable source of data. We therefore plan to survey these audiologists to obtain this information.

Preliminary Studies

Our team, led by [name] (Co-Investigator on this proposal) has completed two RCTs evaluating combination instruments (hearing aids with a built-in sound generator) for bothersome tinnitus in non-hearing-aid users who were candidates for hearing aids based on their hearing loss^{10, 11}. For both studies, participants used combination instruments either with the sound generator activated or deactivated. For one of the trials, a third group used deep-fit, extended-wear hearing aids¹¹. Outcomes for each study were assessed pre- and post-treatment using the Tinnitus Functional Index (TFI)²⁰. Both RCTs revealed comparable findings: every device studied resulted in decreased tinnitus handicap as measured by the TFI. No significant differences in outcomes were observed between groups.

A caveat should be noted concerning these two RCTs: All participants had both hearing loss and bothersome tinnitus. People will often respond to questions about effects of tinnitus with respect to their hearing loss²¹. For some of the participants, baseline to post-treatment improvement on a tinnitus outcome questionnaire would have resulted from improved hearing. Hearing loss, therefore, confounded the results of these studies, and it is impossible to know how much of the improvement in effects of tinnitus was actually a reduction in hearing difficulties.

This pilot study will specifically look at the use of hearing aids to address bothersome tinnitus in Veteran patients who have hearing within normal limits through 4 kHz based on a conventional audiogram. As already described, such utilization of ear-level devices has anecdotal evidence, but no controlled trials evaluating their efficacy for this purpose. This study will obtain initial data with this population of Veteran patients to determine the feasibility and acceptability of this approach. It is anticipated that results will be positive, which will lead to a

future RCT to fully evaluate such an approach to tinnitus management in this under-served population.

Research Design and Methods

Hearing Aid Study

Assessment Visit (Visit 1). After qualifying over the telephone, individuals will be scheduled for an appointment (Visit 1) at the NCRAR to undergo an assessment to determine study candidacy. Following informed consent, participants will complete standard audiologic testing (air and bone conduction hearing thresholds, speech audiometry, immittance audiometry, and hearing aid assessment). During the audiologic exam, any physical issues that would interfere with the participant wearing hearing aids will be identified, and may result in exclusion from participation. If participants meet all criteria, and they are willing to participate, they will be enrolled in the study. Once enrolled, participants will complete the Tinnitus Functional Index (TFI)²⁰, the Hearing Handicap Inventory (HHI), and Tinnitus Questionnaire Baseline.

Enrolled participants (N=20) will be fit with commercially available receiver-in-canal (RIC) hearing aids with optional sound generator and streaming at the first study visit. Participants will be fit using manufacturer-provided ear-domes. Using the NAL-NL2 formula²², real-ear measures, in addition to patient feedback, will be used to verify and adjust the amplification settings. The hearing aids will be adjusted to be acoustically transparent for loud sounds (no loud sounds will be amplified), while providing mild amplification based on NAL-NL2 targets for soft and moderate inputs. The instruments will have data-logging capability, i.e., the number of hours the devices are used per day will be logged for later retrieval by the audiologist. Tinnitus counseling will occur immediately following the fitting and adjustment of the instruments.

All participants will receive scripted tinnitus counseling, which was used in our two previous hearing aid studies^{10, 11}. The counseling, which describes how sound can be used to improve comfort with tinnitus, will follow pp. 31-64 in the flip-chart counseling book *Progressive Tinnitus Management: Counseling Guide*²³, and will require about 15 minutes.

Follow-up Visit (Visit 2). Two to 3 weeks after the fitting, participants will return for a follow-up appointment (Visit 2). The tinnitus counseling will be reviewed for all participants. The research audiologist will check the performance of the hearing aids, retrieve the data-logging information, and provide any necessary instructions to participants to ensure they are using the devices properly. If needed, adjustments will be made to the gain settings of the hearing aids.

Final Visit (Visit 3). Approximately 3 months after Visit 1, participants will return for their final visit (Visit 3). Hearing and speech testing will be repeated at this visit. Hearing testing at the final visit will include only testing of air conduction thresholds. Participants will also complete the TFI and other outcome measures, and answer a series of open-ended questions (Exit Interview). Questions will be asked to determine their subjective impressions of using the devices (general impressions of the devices, if they helped their tinnitus, when they were/were not helpful, and other comments). A final hearing aid check will be completed at this time, and data-logging information will be retrieved. Participants will be allowed to keep their devices, if desired.

Payment. Participants will be paid \$20 for each study visit. Candidates who screen fail at the assessment appointment will still be paid \$20 for coming in.

Outcome Measures. The primary outcome measure will be the TFI, which has been validated for measuring changes in tinnitus impact (*responsiveness*) resulting from intervention²⁰. The 25-item TFI provides an index score from 0-100, with higher numbers reflecting greater tinnitus impact. The developers of the TFI provided data supporting a

minimum TFI score reduction of approximately 13 points as being generally meaningful to an individual patient.

The QuickSIN™ assesses speech understanding in noise²⁴. Participants will listen to sentences at six signal-to-noise ratios (SNRs) presented binaurally in the sound field from a single loudspeaker located at 0 degrees azimuth. An 'SNR loss' is computed with a lower score indicating better performance. The SNR loss is the dB SNR relative to the SNR required for normal hearing individuals to repeat back 50% of the key words correctly. The QuickSIN will be conducted for unaided listening and aided listening at visits one and three. Two lists will be presented and an average score will be computed for each listening condition.

The HHI assesses hearing handicap and will be used to measure the impact of the devices on auditory hearing handicap. The 25-item Hearing Handicap Inventory for Adults (HHIA)²⁵ will be completed by individuals age <65 and the Hearing Handicap Inventory for the Elderly (HHIE)²⁶ will be completed by individuals age 65 years and older. The HHIA and HHIE differ in three questions. Participants answer 'No,' 'Sometimes,' or 'Yes' to a series of statements. Scores are summed across responses with total scores ranging from 0 (no hearing handicap) to 100 (maximum hearing handicap). The HHI will be administered at visits one, two, and three.

The International Outcome Inventory for Hearing Aids (IOI-HA)²⁷ is a seven-item questionnaire that assesses hearing aid outcomes on seven dimensions: Use, Benefit, Residual activity limitation, Satisfaction, Residual participation restriction, Impact (of hearing impairment) on others, and Quality of life. Responses are provided on a 5-point scale. Total scores range from 7 to 35, with higher scores indicating better outcome. The IOI-HA is used routinely in VA clinics to assess hearing aid recipients. This questionnaire will be administered at Visit 3 only.

Statistical Analysis. All quantitative and qualitative data will be provided to the data manager, who is responsible for developing and maintaining study databases and records. The data manager will perform double entry of the questionnaire data to check for and remediate any errors. The primary goal of Aim 1 will be to provide a preliminary evaluation of benefit of low-gain amplification for all participants. The primary outcome measure for estimating benefit of low gain hearing aids for tinnitus will be the TFI. Secondary outcome measures, including the HHIA and the QuickSIN test, will be used to evaluate any changes in perceived hearing handicap, and speech understanding resulting from the intervention. These outcomes will be evaluated at baseline (pre-randomization) and at two follow-up time points post-intervention (i.e., after fitting hearing aids). A linear mixed-model approach will be used to analyze outcome data²⁸. This approach will model an overall baseline mean, along with a mean at each follow-up time point. The same model set up will be used for each outcome measure (TFI, HHIA, and QuickSIN). Contrasts between the follow-up mean estimates and baseline mean will indicate the level of benefit given by the treatment.

Usage of and reactions to wearing the hearing aids will be assessed with both qualitative (exit interview) and quantitative (usage via data-logging) measures. Qualitative analyses of exit interview responses will summarize patient experiences using the devices (e.g., comfort level with wearing the hearing aids, as well as comfort with the amplification, whether there was any sense of stigma from wearing hearing aids, etc.), and self-assessment of benefit. These analyses will follow a similar approach to those described for Aim 2 below. Comparison of the interview responses with actual usage data will provide some validation to self-reported compliance.

VA Clinician Interviews

The Principal Investigator (PI) will email approximately 200 VA audiologists via the National Audiology listserv with the following text:

Please do not “reply all.”

Do you fit hearing aids on Veterans with normal hearing thresholds (25dB HL or better) from .25 kHz through 4 kHz for the purposes of improving quality of life with bothersome tinnitus?

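### For TFI and HHI, the one-arm change from baseline is read as treatment benefit, but it estimates only uncontrolled change under hearing aids plus counseling

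*Combined protocol and SAP*

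**What the plan says.** The Statistical Analysis section for the hearing aid study sets the target: "The primary goal of Aim 1 will be to provide a preliminary evaluation of benefit of low-gain amplification for all participants". It then names the primary measure: "The primary outcome measure for estimating benefit of low gain hearing aids for tinnitus will be the TFI". The secondary outcomes, HHI (named there as HHIA) and QuickSIN, "will be used to evaluate any changes in perceived hearing handicap, and speech understanding resulting from the intervention". The model is a linear mixed model: "This approach will model an overall baseline mean, along with a mean at each follow-up time point". The reading rule follows: "Contrasts between the follow-up mean estimates and baseline mean will indicate the level of benefit given by the treatment".

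Similar wording appears elsewhere. Under Outcome Measures, the HHI "will be used to measure the impact of the devices on auditory hearing handicap". Specific Aims/Purpose promises "preliminary data on the impact of providing mild amplification on perceived tinnitus handicap and perceived hearing handicap in the population being studied".

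On design, the Step-by-Step Guidance (Initial Appointment) gives hearing aids to every participant. The Assessment Visit (Visit 1) text has participants complete the baseline TFI and HHI on enrollment. They are then fitted with devices that have an optional sound generator and streaming, and scripted counseling on using sound for tinnitus follows at once. The Follow-up Visit (Visit 2) text and the Schedule of Tests/Outcomes repeat the counseling at 2-3 weeks.

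**The concern.** The rule turns a before-after difference into a statement of benefit. Several things besides amplification begin at or after the baseline questionnaire, and no participant goes without them: counseling, possible use of the sound generator or streaming, the passage of time, and the expectation that comes with receiving a device. No passage tells the analyst to limit the reading of the contrast for any of these.

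Scientific Rationale and Significance says the pilot data should help decide whether an RCT is warranted and how to run it. If the change in the primary outcome is carried forward as benefit of the treatment, both decisions rest on a quantity that the design does not estimate.

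**Working it through.** The plan states no effect size, SD, alpha or power, so there is no figure to reproduce. The check is what the contrast can identify.

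**Inputs from the documents.** One arm; TFI and HHI at baseline, 2-3 weeks (V2) and about 3 months (V3); device and counseling both begun after the baseline questionnaires; a model with one mean per time point.

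**Expected means.** Let a be the amplification effect. At visit j, let c_j be the counseling effect, g_j the effect of any sound-generator or streaming use, and t_j the time and expectation effects.

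- Baseline: μ
- V2: μ + a + c_2 + g_2 + t_2
- V3: μ + a + c_3 + g_3 + t_3

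Three means give two contrasts:

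- V2 − baseline = a + c_2 + g_2 + t_2
- V3 − baseline = a + c_3 + g_3 + t_3

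**Amplification effect.** Replace a by a + k, t_2 by t_2 − k and t_3 by t_3 − k. All three means are unchanged for every k, so the data cannot separate a from t_j.

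**Package effect.** Let p_j = a + c_j + g_j. Replace p_j by p_j + k and t_j by t_j − k. Again nothing observable changes. Only p_j + t_j is estimable.

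**The same in matrix form.** The rows are the three time points. The columns are intercept (1,1,1), device (0,1,1), counseling (0,1,1), V2 time (0,1,0) and V3 time (0,0,1): 5 columns, rank 3. Device = V2 time + V3 time, so it is not estimable. Recoding counseling does not help, because intercept, V2 time and V3 time already span all three rows. Sample size does not enter.

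**If time and expectation effects were assumed to be zero.** The package effect would then be estimable. Separating device from counseling would depend on the coding. With counseling as (0,1,1), intercept, device and counseling have rank 2 of 3, so only the sum is estimable. With counseling counted by session as (0,1,2), the rank is 3 of 3, but only by assuming a linear effect per session, which the plan does not state. The conclusion does not rest on this step.

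**Illustration on assumed values.** The SD of TFI change (15, 20, 25 points) and the non-amplification improvement b (5, 10, 13 points) are assumptions, not trial figures. With n = 20 and a paired-t approximation, the 95% CI half-width is 2.093 × SD/√20, which gives 7.0, 9.4 and 11.7 points. Set a = 0. The chance that the interval lies wholly on the improvement side comes from a noncentral t with 19 df and noncentrality b√20/SD:

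| b | SD 15 | SD 20 | SD 25 |
|---|---|---|---|
| 0 | 2.5% | 2.5% | 2.5% |
| 5 | 29.3% | 18.5% | 13.3% |
| 10 | 80.7% | 56.4% | 39.7% |
| 13 | 95.7% | 78.7% | 59.8% |

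The table shows only that an apparent benefit can arise with no amplification effect. It does not say how large b is.

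**The case against.** The strongest reply is that this is openly a one-arm pilot. Specific Aims/Purpose says it tests no hypothesis, the evaluation is called preliminary, and Preliminary Studies and Benefits leave full evaluation to a later trial. That stands and lowers the weight. But a preliminary label speaks to certainty, not to what the contrast measures.

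A second reply is that the treatment may fairly mean the whole package. That is a reasonable reading, but the package effect is not identified either.

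A third is that the plan does not rest on the TFI contrast alone. The Final Visit and Statistical Analysis sections describe an exit interview on device impressions, when the devices helped, comfort, stigma and self-assessed benefit, compared with logged usage. This is useful device-specific evidence, but it does not make the contrast causal.

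A fourth is that Scientific Rationale and Significance cites a study of ear-level devices in which controls without devices did not improve. This argues against a large time effect, but it is a different study and the text does not say whether those controls were counseled.

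Some stronger inferences go too far:

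- A reader might infer that any fall in TFI or HHI will be reported as a benefit of amplification. The rule says the treatment, and no passage sets such a reporting rule.
- A reader might infer that Aim 1 is itself a causal claim. Its wording is temporal: it measures a reduction when amplification is provided.
- A reader might infer that the sound generator contaminates the result. It is optional, so its use is possible, not certain.
- A reader might extend the point to QuickSIN, or treat QuickSIN as a clean causal comparison. Neither follows. "The QuickSIN will be conducted for unaided listening and aided listening at visits one and three", so a same-visit comparison exists, but the order of testing is not stated.

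**Conclusion.** The concern holds for TFI and HHI, with minor to moderate weight. As written, the reading rule attaches a benefit to a contrast that estimates only package plus time and expectation change. This follows from the single arm and the shared timing of device and counseling. It needs no assumed figures and holds at any sample size.

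A reader might go on to infer that the design is invalid, that a control arm is required, or that the expected improvement is mostly counseling. The documents support none of these. One arm is legitimate for feasibility and acceptability. The documents give no size for the counseling, time or expectation effects, and they state no TFI threshold for going on to an RCT. Only the stated interpretation is unsupported.

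**What to change.** In the hearing aid study's Statistical Analysis section, replace the sentence on contrasts with:

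> For TFI and HHI, contrasts estimate mean within-participant change from baseline, with 95% confidence intervals, under hearing aids plus counseling (and any sound-generator or streaming use), including any time and expectation effects; without a control group they will not be interpreted as an effect of amplification or of the treatment package.

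Then bring five phrases into line, for example by describing the change in each measure after fitting and counseling:

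- the two sentences on benefit in the same section (goal of Aim 1; primary outcome measure);
- the end of the sentence on secondary outcomes, which attributes changes to the intervention;
- the HHI sentence under Outcome Measures that credits the devices;
- the statement of purpose in Specific Aims/Purpose that refers to the impact of amplification.

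Delete *pre-randomization* from the description of baseline, since nothing is randomized. Aim 1 can stay as it is.

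Optionally, note at the existing Visit 2 and Visit 3 device checks whether the sound generator and streaming were activated, and report this descriptively. The plan describes logging of daily hours only, so this may have to be noted by hand.

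The cost is six rewordings and one deletion, plus the optional short entry at two existing checks. No visit, arm or participant is added. The downside is a less favourable claim from the pilot.
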